#### **Study visits:**

In addition to the intervention, all participants will be seen at 3, 6, 9, 12, and 18 months post baseline for research follow ups. Participants enrolled after 4/1/2019 will only be seen at 3, 6, 9, and 12 months post baseline for research follow ups. These will be done at the CMCVAMC and will take approximately 1.5 hours. The schedule of assessments (all of which are for research purposes only and not part of standard care) is as follows: SCID and MINI (B); Blood samples (%dCDT and GGT) (B and 18m); Time Line Follow-Back, SIP (B, 3, 6, 9, 12, 18); Drug urine toxicology tests (B, 3, 6, 9, 12, 18); Self-efficacy, Coping, Social Support, Readiness to Change, pain, depression, quality of life (B, 3, 6, 9, 12, 18).

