#### **U. Risk/Benefit Assessment**

1. **Potential Study Risks**
  - 1.1. Describe and assess all of the following risks that may be associated with the research:
    - 1.1.1. **Physical There is a small chance of mild pain and swelling where the needle enters the skin and vein, bruising, infection and possibly fainting during the blood draws at baseline and 18 months. Texting (reading and sending) while driving may potentially lead to automobile accidents and bodily injury.**
    - 1.1.2. **Psychological There is a small chance that talking about their personal history can be embarrassing and/or lead to psychological discomfort.**
    - 1.1.3. **Social There is slight risk of embarrassment in terms of coming to the MIRECC suite for the research as MIRECC is geared towards research with mental illness and the stigma associated with mental illness.**

- 1.1.4. Economic **There is no foreseeable economic risk to participation.**
- 1.1.5. Monetary **The Veteran will not have to pay for treatment or participation but will need to pay for transportation to get to the research visits.**
- 1.1.6. Legal **There is no foreseeable legal risk associated with the research. In Pennsylvania it is illegal to text while driving.**
- 1.1.7. Loss of confidentiality **In all research, indeed in all situations, there is a risk of a loss of confidentiality. For instance, if the participant does not have a password on their phone, anyone could pick up their phone and be able to read their confidential messages. This is of incredible importance to the research team and confidentiality will be closely guarded. We will guard participants' information through secure servers (for web-based data) and in locked cabinets in with the MIRECC suite (for paper-based data). In addition, there is the risk that a person authorized to access the text messages might use them for an unauthorized purpose or disclose them to an unauthorized party.**
- 1.1.8. Assess the likelihood and seriousness of such risks. **Low.**
- 1.1.9. Other **N/A**

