- 4.2. Define plans for data and statistical analysis, including key elements of the statistical plan, stopping rules and endpoints.
  - a. Primary objective: The responses for the primary hypothesis comprise five repeated binary measurements per participant indicating risky alcohol use over the follow-up points. Our main analyses will use mixed effects logistic regression models to compare the two groups on the rates of risky alcohol use. We expect that linear and quadratic trends will account for the patterns of use across time. If residual analyses suggest significant lack of fit, we will examine more general time trends using spline specifications. The main explanatory variable will be a binary factor indicating intervention group, together with terms for time trends, and for group by time interactions, if appropriate. Based on analyses of similar data, we expect that a random intercept model, possibly with an autoregressive repeated measures structure, should provide a good fit to the covariance structure of the repeated measures, although we will examine more general specifications, if necessary. The estimated regression coefficients for the group variable, and possibly for group by time interactions, will address our primary hypothesis. We will test whether estimated coefficients are different from zero, and will report estimates and approximate 95% confidence intervals.

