  - b. Secondary outcomes. For Hypothesis 1, we will use the same type of mixed effects logistic regression models as described above to compare the groups on urine toxicology tests for use of drugs other than alcohol. The frequency of heavy drinking is a count response, so we will use mixed effects Poisson regression models to compare two groups on the number of heavy drinking days in a week. The models will allow for over dispersion by including estimation of a variance inflation factor or, if this is insufficient, by considering mixed effects negative binomial regression models. Some subjects have more days without heavy drinking than would be expected under a Poisson model. To account for this, we will fit mixed effects zero inflation models. If levels of heavy drinking are too low even for zero-inflation models, we will compare the intervention groups on the absence or presence of any heavy drinking days in a week, using mixed effects logistic regression models. Measures of depression and pain, and biological measures of alcohol use, will be continuously distributed, and will be compared across the groups using mixed effects linear regression models, after transformation of these responses to approximate normality. The explanatory variables, time trends, and covariance structure for these secondary analyses will be chosen as described for the primary hypothesis.

We will follow a similar approach for testing Hypothesis 2, using data generated by electronic medical records to count the number of opioid overdoses for each participant through the course of the trial. We expect low rates of OD, so we will compare the groups on the rates of having an OD via a logistic regression model. If the numbers of OD are sufficiently high, we will compare the groups using Poisson or Negative Binomial models for the total number of OD per participant across the trial.

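### The %dCDT and GGT analysis borrows a five-visit trend model for an outcome drawn only at baseline and month 18, and leaves the role of baseline and the tested coefficient unstated

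*Combined protocol and SAP*

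**What the plan says.** **Model.** Section W, item 4.2.b handles the markers together with depression and pain: "Measures of depression and pain, and biological measures of alcohol use, will be continuously distributed". All of them go to mixed-effects linear regression after transformation towards normality, and the paragraph closes with "The explanatory variables, time trends, and covariance structure for these secondary analyses will be chosen as described for the primary hypothesis".

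**What is borrowed.** Item 4.2.a describes the primary responses as "five repeated binary measurements per participant indicating risky alcohol use over the follow-up points". On time it says "We expect that linear and quadratic trends will account for the patterns of use across time", with splines if the fit is poor. The group factor enters "together with terms for time trends, and for group by time interactions, if appropriate". The covariance is a random intercept, with an autoregressive structure as a possibility. The hypothesis is tested on the group coefficient and possibly on group by time.

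**Sampling.** The schedule under Study visits in section O reads "Blood samples (%dCDT and GGT) (B and 18m"; depression and pain are measured at baseline, 3, 6, 9, 12 and 18 months. The physical-risk statement in section U agrees: "possibly fainting during the blood draws at baseline and 18 months". Section O also states: "Participants enrolled after 4/1/2019 will only be seen at 3, 6, 9, and 12 months post baseline for research follow ups".

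**The concern.** Depression and pain have the repeated follow-up values that the borrowed model needs. The two blood markers have one each. The plan therefore assigns them a trend and covariance structure that their data cannot support. It does not say whether the baseline marker is a covariate or a response, or which coefficient answers the hypothesis.

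The markers matter because they are named in secondary Hypothesis 1 (section J) and are the only objective measures of alcohol use listed; urine toxicology is for other drugs. The primary outcome is self-reported by timeline follow-back, and the March 2018 amendment in section O allows that some Veterans may under-report drinking. The markers are the natural check on that outcome, so the analysis should not leave open whether it estimates the whole effect, part of it or none.

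**Working it through.** The documents give no sample size, power, SD or effect for either marker, so there is no planned figure to reproduce. The check covers what can be estimated, what each candidate coefficient targets, and the resulting power.

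**1. Fixed effects.** Columns: intercept, group g, time t, t².

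- Five follow-up visits (3, 6, 9, 12, 18): rank 4 of 4; with g·t and g·t², 6 of 6. Estimable.
- Month 18 only: t and t² are constants, so rank is 2 of 4 (2 of 6 with interactions). No time term is estimable.
- Baseline and month 18 (t = 0, 18): t² = 18t at both points, so rank is 3 of 4 (4 of 6). Linear time and group by linear time are estimable; the quadratic terms are not.

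**2. Covariance.** With one value per person, the random-intercept and residual variances appear only as a sum. With two values, a random intercept (variance σb²) plus autoregressive residuals (variance σe², correlation φ) has three parameters, but the data give two quantities: variance σb² + σe² and covariance σb² + φσe². The combination is not identifiable.

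**3. What each coefficient targets.** Let δ be the true group difference at month 18, with no difference at baseline (randomisation).

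- Month-18 value on group, with or without baseline as a covariate: δ.
- Both draws as responses, linear time, group by time: 18 × interaction = δ. The group coefficient is 0 if time is counted from baseline and δ/2 if time is centred at 9 months.
- Both draws as responses, no interaction: (0 + δ)/2 = δ/2 with complete pairs, at any correlation.

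If only a fraction p has the month-18 draw, equally in both arms, the last coefficient becomes δ × p / [2p + (1 − p)(1 + ρ)], where ρ is the baseline-to-month-18 correlation. At p = 0.8 (the 20% dropout by month 18 in item 4.1) and ρ = 0.5: 0.8 / (1.6 + 0.3) = 0.42. At ρ = 0.3 and 0.7 it is 0.43 and 0.41. At p = 0.5 (assumed) it is 0.30, 0.29 and 0.27 for ρ = 0.3, 0.5 and 0.7.

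**4. Power.** Assumptions: unit SD at both draws, n complete pairs per arm, two-sided 5% (the plan states 5% for the primary outcome only). For the markers ρ is not given; 0.3, 0.5 and 0.7 are assumed. Variances:

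- ANCOVA (month 18 given baseline): 2(1 − ρ²)/n
- Month 18 only: 2/n
- Group by time: 4(1 − ρ)/n
- Additive group coefficient: (1 + ρ)/n, with target δ/2

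Fix δ so that ANCOVA has 80% power, that is δ/SE = 1.96 + 0.84 = 2.80. The other signal-to-noise ratios are 2.80 multiplied by √(1 − ρ²), √((1 + ρ)/2) and √((1 − ρ)/2) respectively; n cancels.

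| ρ | ANCOVA | Group by time | Month 18 only | Additive group |
|---|---|---|---|---|
| 0.3 | 80% | 62% | 76% | 38% |
| 0.5 | 80% | 68% | 68% | 29% |
| 0.7 | 80% | 73% | 52% | 19% |

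Example, additive at ρ = 0.5: 2.80 × √(0.5/2) = 1.40; 1.40 − 1.96 = −0.56; Φ(−0.56) = 0.29.

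**5. Simulation.** In 200 simulated trials with 75 per arm (half of the 150 due to enter treatment), ρ = 0.5 and δ = −0.50 SD, the additive group coefficient averaged −0.24 with power 39%. The interaction averaged −0.51 with power 88%. Both agree with step 3.

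**The case against.** The plan describes how terms will be selected rather than one fixed model. Interactions enter where suitable and may carry the test, and an analyst would notice and drop terms that cannot be estimated. On the literal reading of item 4.2.a, responses are follow-up values only; dropping the inestimable terms leaves a regression of the month-18 value on group, which is unbiased with complete data. If baseline is added as a response together with group by time, the interaction recovers the whole effect.

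That argument stands against a stronger conclusion that a reader might draw: that the biomarker analysis must either fail to run or be biased by about half, so that a real effect would probably be reported as uncorroborated. The documents do not support this. Halving needs choices that the plan nowhere states: baseline entered as a response, and either no interaction or a group coefficient read with time centred midway.

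The argument does not remove the gap. The coefficient that the plan names without qualification is the group coefficient, and in an interaction model with time counted from baseline that coefficient targets zero. The valid routes also differ in precision, and nothing in the plan selects among them.

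**Conclusion.** The concern holds as a specification gap. The trend and covariance structure assigned to %dCDT and GGT cannot be applied to one post-baseline draw, and its quadratic and combined covariance terms are not identifiable even with both draws. The unstated choices decide whether the tested coefficient targets all, half or none of the month-18 effect; the half becomes about 0.41 to 0.43 if 20% of month-18 draws are missing. Against a baseline-adjusted comparison with 80% power, the valid alternatives have between 52% and 76% and the additive coefficient between 19% and 38%. These figures rest on the assumed correlations, equal variances and no true baseline difference; the power figures also assume complete pairs.

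Participants enrolled after 4/1/2019 have no scheduled follow-up draw. They add nothing directly to a month-18 comparison and would dilute the additive coefficient further. Their number is not given. The primary analysis is unaffected. The change is worth making because the markers are the only objective check on self-reported drinking and the remedy uses data already scheduled.

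**What to change.** In section W, item 4.2.b, take %dCDT and GGT out of the sentence that assigns mixed models. For each marker, specify a linear model of the transformed month-18 value on intervention group and the baseline value under the same transformation, with no time terms and no repeated-measures covariance, and name the group coefficient as the test. The transformation towards normality already planned is enough; log is one option. Keep the mixed models for depression and pain. Add that participants enrolled after 4/1/2019 have no scheduled follow-up draw and so do not contribute to this comparison.

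A group-by-time or month-18-only analysis would also be valid. The baseline-adjusted model is preferred because it is at least as precise as either and leaves only one coefficient to read. The cost is two or three sentences, with no new data, visits or procedures.

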e. **Summary of Findings from Our Research Program.** These studies demonstrate our ability to recruit large samples in a timely fashion, enroll Veterans who are engaging in risky drinking into research studies, deliver interventions over the telephone, and maintain high follow-up rates across periods as long as 24 months. Three of these studies also provide evidence to support the effectiveness of enhanced or extended interventions for patients who do not evidence a good initial response to alcohol/drug treatment.

I. **Purpose of the Project:** (Clearly provide the purpose of this research project.) In this application, we propose to test an integrated prevention intervention, designed to reduce rates of risky drinking in Veterans receiving prescription opioids for chronic pain management or opioid replacement therapy. For Veterans on opioid replacement therapy, they must have a chronic pain diagnosis. This adaptive, patient-centered intervention provides integrated clinical assessment, brief intervention, monitoring, and extended prevention services delivered through a combination of telephone calls, and text messages.

J. **Describe the Research Questions or Hypotheses** (that is, what questions are you trying to address by conducting the research.)

1. **Primary objective:** To compare the effectiveness of a 12-month prevention intervention (PI) with a brief intervention only group (BIO) over an 18-month follow-up period, for Veterans treated with prescription opioids and who are engaging in risky/hazardous drinking, based on NIAAA guidelines.
  - *Hypothesis 1:* PI will produce better outcomes than BIO, as indicated by lower rates of risky/hazardous alcohol use across the follow-up period.
2. **Secondary objectives:** To examine secondary outcome measures, moderator effects, and mediation effects:
  - *Hypothesis 1:* PI will produce better outcomes than BIO on frequency of heavy drinking, biological measures of heavy drinking (i.e., GGT and CDT), urine toxicology tests to assess other drug use, depression, and pain.
  - *Hypothesis 2:* Rates of opioid overdoses will be lower in PI than in BIO
  - *Hypothesis 3:* Intervention effects will be greater in higher-risk Veterans, including those with higher prescription opioid dosages, co-occurring benzodiazepine use, poor social support, and low readiness for change.

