As part of broadening the inclusion criteria we plan to add a third group to the adaptive intervention. We will enroll and randomize the Veterans who do not admit to drinking and place them in a monitoring category where we continue to assess them and if they admit to consuming any amount of alcohol we would then transfer them to the treatment arm into which they had been randomized. This change is a significant change to the study but does not change the aims or outcomes and it does not increase the risk. It is a change supported by the DOD as a way to increase enrollment and reach veterans that we think may be less truthful about their alcohol use out of fear that they will have their opiate prescriptions taken away.

Following up those who initially deny drinking will provide important data for the VA. The yearly AUDIT screening appears to be underestimating the numbers of vets who are drinking alcohol. If our data indicate that a significant percentage of those who deny drinking at the start of the study end up reporting drinking later in the follow-up, it will be in indication that at risk patients (i.e., those on opioid meds) are at risk due to underreporting of their drinking, which could be an unintended consequence of the current VA policies.

We also will no longer be using the AUDIT-C.

Additionally, we have decreased the total n for the study to 150 from all sites. That is, 200 subjects from all sites being randomized (with 150 participants drinking and entering TX phase and 50 participants not drinking (25 at CMCVAMC and 25 at Penn).

Moreover, there is a personnel change. [name] is no longer a Research Coordinator on this study.

Lastly, SenseHealth has changed its name to Wellpass and the TRC has moved its location to [name]

At the time of this amendment, the following number of subjects have been randomized at the following sites:

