#### R. Subject Recruitment (characteristics of the study population)

1. Provide the planned or targeted enrollment at:
  - 1.1. CMCVAMC - 115 (90 undergoing treatment and 25 just being followed and not undergoing one of the treatment groups)
  - 1.2. Other sites - 60 (10 at VA Pittsburgh; 50 at Penn)
  - 1.3. Not applicable; chart review or use of previously collected data -

2. **Screening and/or Eligibility Requirements - Inclusion/exclusion criteria are the same for screening before and after consent, however, some assessments used to determine final eligibility (such as the SCID and the MINI) are only administered once the Veteran comes to the lab (which occurs after a positive phone screen)**

2.1. Describe and provide justification for:

2.1.1. Inclusion criteria: **To be eligible for participation, Veterans must: (1) currently be receiving daily treatment with a prescription opioid for chronic pain, OR receive a daily prescription for opiate replacement therapy and have a chronic pain diagnosis; (2) be between the ages of 18 and 75; (3) have a cell phone capable of receiving text messages; (4) and be willing to be in a study where they might receive text messages.**

**If at some point during follow-up research visit, if a subject admits to drinking they will move on to the treatment arm that they were randomized to upon entry into the study.**

2.1.2. Exclusion criteria: **Veterans will not be eligible if they: (1) meet DSM-V criteria for a moderate to severe alcohol or drug disorder (with the exception of nicotine abuse/dependence); (2) have a current psychotic disorder severe enough to require inpatient treatment; or (3) are participating in alcohol use treatment at the VA or elsewhere (with exception of screening and brief intervention at the VA); (4) are currently on palliative care or are being treated with opioids for cancer-related pain.**

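### The overdose comparison (Hypothesis 2) names no method for sparse events; a logistic fit with Wald inference gives no usable result if one arm has no overdose

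*Combined protocol and SAP*

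**What the plan says.** Section J.2 states secondary Hypothesis 2: "Rates of opioid overdoses will be lower in PI than in BIO". Section W.4.2.b gives its analysis: "We will follow a similar approach for testing Hypothesis 2, using data generated by electronic medical records to count the number of opioid overdoses", with one total per Veteran. It then says "We expect low rates of OD, so we will compare the groups on the rates of having an OD via a logistic regression model". The alternative, applied to each Veteran's total, reads: "If the numbers of OD are sufficiently high, we will compare the groups using Poisson or Negative Binomial models".

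The style of inference is set in W.4.2.a, for the primary analysis: "We will test whether estimated coefficients are different from zero, and will report estimates and approximate 95% confidence intervals". Hypothesis 2 is linked to the other analyses only by the statement that a similar approach will be followed.

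No exact, penalised, score or profile-likelihood method is named for overdose, and no rule covers an arm with no events. The same section does give heavy drinking a fallback if its levels are too low for the planned count models.

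**The concern.** The plan expects few overdoses. It names one model for that case and one alternative for the opposite case. If either arm has no overdose, the maximum-likelihood estimate of the group log odds ratio is infinite. Software then stops at an arbitrary large value with a huge standard error, and the Wald p-value is close to 1 however many events the other arm has.

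This includes the result most favourable to Hypothesis 2, no overdoses under PI. The analyst would then have to choose another method after seeing the counts, and the candidate methods do not always agree.

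**Working it through.** **Inputs.**
- Arm size: the March 2018 Amendment text in section O gives "200 subjects from all sites being randomized (with 150 participants drinking and entering TX phase", so 75 to 100 per arm if the arms are equal. Section R.1 gives "115 (90 undergoing treatment and 25 just being followed and not undergoing one of the treatment groups") at the lead site and "60 (10 at VA Pittsburgh; 50 at Penn") elsewhere: 115 + 60 = 175, about 87 per arm, which lies inside that range.
- Allocation: two arms by urn randomization (M.2.2); equal arms assumed.
- Alpha: 5% is stated for the primary outcome only (W.1); two-sided 5% assumed here.
- Overdose rate: not given beyond being low. Assumed range: 0.5% to 5% of Veterans per arm over follow-up.

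The plan states no event count or power for overdose, so there is no figure of its own to reproduce.

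**Step 1: chance of a zero arm.** With rate p and n per arm, P(an arm has none) = (1−p)^n. With equal rates, P(at least one zero arm) = 1 − [1 − (1−p)^n]², and P(both zero) = (1−p)^(2n). For p = 1% and n = 75: 0.99^75 = 0.471; 1 − 0.529² = 0.72; 0.471² = 0.22.

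| Rate per arm | At least one zero arm, n = 75 | Both zero, n = 75 | At least one zero arm, n = 100 | Both zero, n = 100 |
|---|---|---|---|---|
| 0.5% | 90% | 47% | 85% | 37% |
| 1% | 72% | 22% | 60% | 13% |
| 2% | 39% | 5% | 25% | 2% |
| 3% | 19% | 1% | 9% | 0.2% |
| 5% | 4% | <0.1% | 1% | <0.1% |

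If PI halves the BIO rate, the chance of at least one zero arm is 1 − [1 − (1−p)^n][1 − (1−p/2)^n], where p is the BIO rate. That gives 95, 83, 59, 39 and 17% at n = 75, and 91, 75, 45, 26 and 9% at n = 100.

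**Step 2: what the fit returns with one zero arm.** Maximum-likelihood logistic fits to 0/75 versus 1 to 7/75 stop at a log odds ratio of −20 to −22, with a standard error of about 15,000 and Wald p above 0.998 in every case. At 100 per arm the standard error is about 13,000 and p is again above 0.998.

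**Step 3: other methods on the same tables (75 per arm).** Firth's estimate for a 2×2 table adds 0.5 to each cell. For 0 versus 6 the odds ratio is (0.5/75.5)/(6.5/69.5) = 0.071.

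| Method | 0 vs 5 | 0 vs 6 |
|---|---|---|
| Wald p | 0.999 | 0.999 |
| Likelihood-ratio p | 0.008 | 0.003 |
| Fisher exact p | 0.058 | 0.028 |
| Firth profile-likelihood p | 0.025 | 0.012 |

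For 0 versus 6 the Firth profile-likelihood 95% interval for the odds ratio is 0.0005 to 0.62. For 0 versus 5, Boschloo's unconditional exact test gives p = 0.041. So five events against none are significant at 5% by some methods and not by others.

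**Step 4: size and power.** Size is the sum, over all pairs of counts, of the two binomial probabilities for pairs where p < 0.05; power is the same sum with the rate halved in one arm. At 75 per arm and rates of 1, 2 and 3%, Fisher's size is 0.01, 0.2 and 0.6%. The Wald test's size is at most 0.1%, counting a zero arm as no rejection. The ordinary likelihood-ratio test errs the other way: its size reaches 9.3% (75 per arm, 3%) and 9.5% (100 per arm, 2%). Fisher's power to detect a halved rate is 0.2% for 2% versus 1%, and 3.7% for 5% versus 2.5%. Even the likelihood-ratio test has only 18% power for 5% versus 2.5%.

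**The case against.** **The reasoning in the text is sound.** A reader might infer that the plan picks logistic regression because it thinks the model suits sparse data. It does not say so. The expectation of low rates justifies a yes/no outcome over a count, and the next sentence keeps the count for numerous events. This stands: the endpoint is right and only the sparse-data method is missing.

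**Maximum likelihood and Wald are inferred.** W.4.2.b says only that a logistic model will be used, and Firth's method is itself logistic regression. The wording on coefficients and approximate intervals belongs to the primary analysis. This also stands, but the inference is the natural one: Hypothesis 2 is to follow a similar approach, and no variant is named.

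**Some inference survives a zero arm.** A reader might conclude that no confidence interval exists at all. That is too strong. For 0/75 versus 6/75 an ordinary likelihood-ratio test gives p = 0.003, with a one-sided profile bound of about 0.36 for the odds ratio. What is lost is the finite estimate and the Wald test and interval. The likelihood-ratio test is not a safe default either, given its inflated size.

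**A zero arm is not certain, and the fix does not rescue every case.** At 5% it is unlikely. At 0.5 to 1% many of the affected trials have no event in either arm, where no method can show a difference.

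**The consequence is limited.** Power is very low with any method, so the conclusion on Hypothesis 2 would seldom change.

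**Conclusion.** The point holds as a cheap improvement to one secondary analysis. With few events in each arm but none at zero, the estimate is finite and the Wald test is conservative, not undefined. With one zero arm, the stated analysis, read as maximum likelihood with Wald inference, returns nothing usable.

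How often that happens depends on an overdose rate that the documents do not give. At least one zero arm is more likely than not at about 1% or below and uncommon at 5%. These figures assume equal arms of 75 to 100.

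Two further readings are not supported. Overdose might be taken for the trial's main patient-safety outcome, but sections J.2 and L list it among the secondary hypotheses and outcomes, and safety is handled through serious adverse event reporting in W.2. Nor is there a general threshold of six events below which the comparison must be descriptive: six against none is where Fisher's test first reaches 5%, while Firth profile likelihood and Boschloo's test reach it at five against none.

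**What to change.** In W.4.2.b, name one method for Hypothesis 2 when overdoses are few: Firth-penalised logistic regression on any overdose versus none, with the penalised profile-likelihood test and 95% interval. A Wald interval around the Firth estimate should not be substituted: for 0/75 versus 6/75 it runs from 0.004 to 1.28, although the profile interval excludes 1. If an exact analysis is preferred, name a single one instead, such as Boschloo's unconditional test with an exact interval for the risk difference. Do not leave the choice open, because the methods can disagree.

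Report the number of Veterans with an overdose by arm in every case, and state that the result is descriptive if neither arm has an event.

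The cost is a few sentences of SAP text, with no change to data collection. The downside is some conservatism, which would be marked if Fisher's test were chosen. The change makes the result reportable but does not make the hypothesis well powered, and the SAP should say so.
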